 - clinically significant apnoea *and/or*
 - clinically significant desaturation *and/or*
 - clinically significant bradycardia
- Apnoea
 - clinically significant apnoea was defined as a pause in breathing, as measured by the Philips cotside monitor, which:
 - lasts more than 15s in duration, *or*
 - was accompanied by clinically significant desaturation and/or bradycardia as defined below, *or*
 - required intervention (manual stimulation, PEEP or IPPV)
- Bradycardia
 - clinically significant bradycardia was defined as heart rate < 100 for $\geq 5s$ as measured by Philips cotside monitor with a 5s averaging time
- Desaturation
 - clinically significant oxygen desaturation was defined as $SpO_2 < 80\%$ for $\geq 5s$ as measured by Philips cotside monitor with a 5s averaging time

Primary Outcomes

This study will measure the number of respiratory events and oximetry histograms during each of the 24h condition periods:

- Number of respiratory events:
 - Defined as total number of clinically significant:
 - Apnoeic events
 - Desaturations
 - Bradycardic events
- Percentage of time spent with $SpO_2 < 80\%$ over the 24h testing period

Secondary Outcomes

- Percentage of time spent with $SpO_2 \geq 88\%$ over the 24h testing period

Effect Size

A clinically significant effect was defined for each of the three outcomes:

- 40% reduction in number of respiratory events
- 50% improvement in percentage of time spent with $SpO_2 \geq 88\%$ over the 24h testing period
- 50% reduction in percentage of time spent with $SpO_2 < 80\%$ over the 24h testing period

Data Collection

The following demographic and clinical data will be recorded for each infant on enrolment in order to describe our sample:

- Gender
- Gestational age at birth
- Chronological age and Corrected gestational age
- Birth weight
- Current weight
- Feed volumes (mL/kg/day)
- Caffeine administration

All infants enrolled in the study will be monitored using the same standard cardiorespiratory monitoring and nursing observations employed for all babies managed in the unit. The following clinical data will be recorded in order to test the primary hypothesis:

- Number of respiratory events

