 - Apnoeas, desaturation and bradycardic events, as defined previously, will be counted and totalled for each 24 hour period by retrospective review of the central monitor. This data will also be reconciled with a nursing observation sheet in order to identify issues with lead contact, cares or events requiring intervention.
- Oximetry histogram
 - The percentage of time spent with oxygen saturations $\geq 88\%$ and $<80\%$ will be recorded using the histogram feature of the Philips monitors at the cot-side at the conclusion of each 24 hour condition period

Blinding

Data collection for number of respiratory events will be blinded, as it relies on examining the monitoring trace for each 24 hour condition period and counting the number of events. While the trace will identify which baby is being monitored, the researcher counting the events will be blind to the test condition for each 24 hour period. The histogram data is completely objective, derived from the monitors, and can be printed at the end of each 24h condition period.

Study Design

Design

This study will employ a randomised triple crossover design. In this approach, each infant will experience each of the three test conditions in a sequence which is randomised. Thus each infant will serve as its own control, and variance within and between infants can be measured. Benefits of a crossover design include smaller sample size requirements compared to equivalent parallel-group trials in order to meet the same criteria in terms of type I and type II error risks³⁹. In addition, each infant is managed equivalently in every respect, excepting the actual order of the test conditions experienced – thus no infant should be advantaged or otherwise relative to the other infants enrolled in the study as each infant is exposed to the same conditions.

In general terms, crossover design is appropriate when:

- The underlying disease is similar during all treatments, i.e. not cured by one of the treatments and not of a short duration relative to the treatment period. It is necessary to separate period effects from treatment effects. This is the case in this study, as we are examining respiratory events which occur as a result of feeding. A feed-related intervention should only have any effect on events during and after the actual feed, and will not be curative of respiratory events in subsequent feeds.

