Nutritional requirements vary with the post-gestational age and condition of any given baby. Most preterm infants will progress temporally from parenteral nutrition (provided through a cannula) to enteral nutrition with a nasogastric tube (feeding tube) to suck feeds (breast or bottle feeding) before being considered suitable for discharge. Nasogastric feeds may be administered continuously by pump (given at a continuous rate measured in mL/hr) or more commonly, bolus (a volume of milk/formula is given at a particular time interval, usually every 2 to 3 hours). Furthermore, bolus feeds may be given by gravity ('as quickly as the tube will accommodate') or pump (a rate can be specified to give the feed over a longer period of time). Most babies begin enteral feeds as bolus feeds with smaller volumes given every 2 hours, and then progress to 3 hourly feeds. Such feeds are usually administered by gravity bolus, however clinical factors may warrant reducing the feed rate (e.g. giving the same bolus volume over 45min).

Infants will undergo test conditions in combinations of feed and position conditions, as outlined in Table 1. Infant and cot positional interventions, where possible, will be maintained throughout the entirety of the 24h condition period, with the exception of routine nursing cares and brief interactions with parents and caregivers.

Table 1: Test Conditions Employed in the FIBRE Study

	Infant Position	Cot Position	Rate of Feed
Condition A Control	Supine	Flat	Bolus gravity feed
Condition B Position intervention	Prone	Propped (15 degrees)	Bolus gravity feed
Condition C Feed rate intervention	Supine	Flat	Continuous pump feed over 45 min

Timecourse

Each condition continues for 24 hours before switching to the next condition. Thus each infant will experience each intervention over a 3 day period of enrolment, with the order of progression through conditions randomly assigned. No washout period will be required between conditions, as respiratory events should be related to the period during and immediately post-feed (i.e. the effect of the previous test condition should have disappeared well before the first feed in the next test condition).

Randomisation

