Infants will be randomly assigned to one of six sequence groups ABC/ACB/BCA/BAC/CAB/CBA, as outlined in Table 2. This will permit assessment of potential period effects and carryover effects, as each treatment follows every other treatment at least once in the six sequence design, as opposed to a simpler Latin Square approach. Randomisation will be achieved through the use of a computer generated sequential list, thus dictating the sequence of conditions.

Table 2: Test Conditions Employed in the FIBRE Study

Group	Sequence Group
1	ABC
2	ACB
3	BAC
4	BCA
5	CAB
6	CBA

Size and Power Considerations

We will use a 5% significance level ($\alpha = 0.05$) for all comparisons. The expected sample was sized using a two-sided test, as there is no strong expectation that effect size would only be in one direction. A small pilot was conducted using $n = 10$ babies using existing monitor data, and measuring three outcomes sequentially over three days for each baby:

- Number of respiratory events (primary outcome)
- Percentage of time spent with SpO₂ < 80% over the 24h testing period (primary outcome)
- Percentage of time spent with SpO₂ \geq 88% over the 24h testing period (secondary outcome)

The observed baseline data was right-skewed, thus a log transformation was applied. The between (σ_s^2) and within subject variance (σ^2) were estimated by fitting a variance components model to the log-transformed baseline audit data for each of the three outcomes.

The sample size formula for a two-sided cross-over study design is shown in Equation 1, where n_c is the minimum total sample size required for cross-over design, and $Z_{\frac{\alpha}{2}}$ and Z_β are the values of the standard normal distribution that cut off probability $\frac{\alpha}{2}$ and β in the upper tail respectively, σ^2 is the within-subject variance and Δ is the minimum difference to be detected. For cross-over studies the variance term depends only on the within-subject variance:

$$n_c = \frac{2 \left(Z_{\frac{\alpha}{2}} + Z_\beta \right)^2 (\sigma^2)}{\Delta^2}$$

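### The respiratory-event count is called blinded because it comes from the trace, but the final count also uses a nursing sheet and bedside interventions by staff who can see the condition

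*Protocol*

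**What the plan says.** **Blinding.** The protocol gives one reason for the claim: "Data collection for number of respiratory events will be blinded, as it relies on examining the monitoring trace for each 24 hour condition period". It adds that "the researcher counting the events will be blind to the test condition for each 24 hour period".

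**Data Collection.** Events are counted by retrospective review of the central monitor, and then: "This data will also be reconciled with a nursing observation sheet in order to identify issues with lead contact, cares or events requiring intervention".

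**Outcomes, Definitions.** An apnoea starts from a pause in breathing measured by the cotside monitor. The pause is clinically significant if it meets any one of three alternatives: it exceeds 15 s, it comes with a qualifying desaturation or bradycardia, or it "required intervention (manual stimulation, PEEP or IPPV").

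**Table 1, Test Conditions.** Condition B is prone in a propped cot, while A and C are supine and flat. Condition C is a "Continuous pump feed over 45 min", while A and B are gravity feeds. Where possible, positioning "will be maintained throughout the entirety of the 24h condition period".

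The protocol does not say who carries out the reconciliation, whether it follows a completed trace count, or whether the sheet shows position or feed method.

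**The concern.** The blinding claim rests on the trace being the source of the count. Two other provisions bring in information from the bedside. One is the nursing sheet, used to identify lead-contact problems, cares and interventions. The other is the intervention criterion, under which some pauses count only because somebody acted. Those who act, and those who fill in the sheet, work beside an infant whose condition is visible. The protocol does not state that they are unblinded, but it follows from Table 1.

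At stake is the credibility of a primary outcome. If a difference in event counts is found, a critic can ask whether it arose from how staff intervened or what they wrote down. The blinding statement does not answer that question, because it covers the person reading the trace and not the information added afterwards.

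**Working it through.** No figure in the protocol is in dispute. The check sets the provisions side by side and then illustrates scale.

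**1. Which parts of the outcome depend on the bedside?**

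| Component | What decides it | Bedside input |
|---|---|---|
| Desaturation (SpO2 below 80% for at least 5 s) | Monitor | Only if reclassified at reconciliation |
| Bradycardia (heart rate below 100 for at least 5 s) | Monitor | Only if reclassified at reconciliation |
| Apnoea over 15 s | Monitor | Only if reclassified at reconciliation |
| Apnoea with qualifying desaturation or bradycardia | Monitor | Only if reclassified at reconciliation |
| Pause of 15 s or less with neither, but with intervention | Monitor for the pause, staff for the act | Yes, by definition |
| Percentage of time in SpO2 ranges | Monitor histogram | None through the sheet |

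The nursing sheet is the only source the protocol names for interventions. The fifth row therefore cannot be completed from the trace reading described under Blinding.

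**2. How large might the effect be? (assumptions, not protocol figures)**

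Suppose staff intervene 1.5 times as often in control as in a test condition, with no true effect, and a share s of events qualifies only by intervention.

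- If s is a share of events in the test condition, the spurious reduction is 1 − 1/(1 + 0.5s): 2.4% at s = 0.05 and 9.1% at s = 0.20.
- If s is a share of control events, it is 1 − [(1 − s) + s/1.5] = s/3: 1.7% at s = 0.05 and 6.7% at s = 0.20.

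The protocol gives neither s nor the 1.5, and reclassification for lead contact or cares is not included.

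**3. What would a bias of a given size do to the test?**

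Inputs from Size and Power Considerations: n_c = 87 for a 40% reduction, two-sided α = 0.05, power 0.80, planned 90 infants. The within-subject variance is not stated, so it is back-solved from Equation 1. This takes n_c = 87 as given and does not verify it.

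- σ² = n_c Δ² / [2(z_{α/2} + z_β)²] = 87 × (ln 0.6)² / (2 × 7.849) ≈ 1.45
- SE of a pairwise log ratio at 90 infants = √(2 × 1.446/90) ≈ 0.179

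If there is no true effect and ascertainment lowers one condition's count by a fraction x, set b = |ln(1 − x)|. The two-sided rejection rate is then Φ(b/SE − 1.96) + Φ(−b/SE − 1.96).

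| Assumed x | Rejection rate |
|---|---|
| 2% | 5.1% |
| 5% | 5.9% |
| 10% | 9.0% |
| 15% | 14.8% |
| 20% | 23.8% |

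**The case against.** The strongest reply is that the blinding sentence is not contradicted. It says that the person counting does not know the condition, and that may be true while the trace is being read. Nothing says that this person reconciles the count or sees a sheet showing position or feed method. That stands. A reader might infer that the counter is unblinded, but the documents do not support it. What fails is the reason given and its extension to the final count.

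Other stronger readings also go beyond the text:

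- **Staff can create events.** They cannot do so alone. A pause measured by the monitor is required first, and the exposed class is residual.
- **The sheet deletes events.** The protocol says it identifies issues; no deletion rule is stated. Exclusion of artefact is a natural reading, but still an inference.
- **The trace identifies the baby.** The protocol says so itself. Each infant receives all three conditions in random order, so identity alone does not reveal the condition in a given period.
- **The bias favours the hypothesis.** The aims do hypothesise fewer events, but the protocol also reports no consensus on practice and no strong expectation of direction when sizing the trial. Less stimulation could let a pause run past 15 s or reach desaturation and so count anyway; more stimulation in control could cut events short.
- **The bias is 2 to 9%.** That range depends on two assumed inputs and on the denominator chosen for s.

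It is also fair that the other primary outcome, time with SpO2 below 80%, does not use the sheet and gives a partial check. Sheet layout is often left to a study manual. The blinding claim, the data sources and the outcome definition, however, are fixed in this protocol and do not fit together.

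**Conclusion.** The point holds in a limited form. The blinding described can apply to reading the trace but not to the final event count, because reconciliation and the intervention criterion bring in information from staff who can see the condition. The exposure is partial: intervention-only apnoeas, and any events reclassified for lead contact or cares.

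Neither the size nor the direction of bias can be derived from the documents. Under the assumptions above, a spurious difference below 10% is small beside the 40% target effect and leaves the error rate at or below about 9%; larger differences would matter more. This does not undermine the trial. It is a stated property of a primary outcome that the design does not fully have, and it is cheap to repair.

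A reader might go further and conclude that the primary outcome must be redefined on monitor criteria alone. The documents do not require that. It would drop apnoeas that the protocol regards as clinically significant, which is a trade-off and not a correction.

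**What to change.** 1. In Blinding, limit the claim to the reading of the trace, and state who reconciles and with what information.
2. Have the blinded researcher count events by monitor criteria only (duration, SpO2, heart rate) and lock that count before seeing any nursing data.
3. Reconcile afterwards from an extract of the sheet that holds only clock times of lead-off, cares and interventions, with position and feed information removed.
4. Keep the primary definition. Report by condition the apnoeas that qualify only by intervention and the events removed at reconciliation. Prespecify the locked monitor-criteria count as a sensitivity analysis.

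The cost is a little extra data handling and one extra analysis. No additional reader is needed and the sample size is unchanged.

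Two limits remain. The extract protects the counter, but the nurse's own entries are still made with the condition in view. The sensitivity analysis addresses this because it uses none of those entries. That locked count will still contain lead-contact and handling artefact, and it cannot undo any effect of an intervention on the trace itself, so it complements the reconciled count and does not replace it.

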Aims / Hypothesis

This study aims to determine the effects of feeding interventions (infant and cot positioning, pump vs gravity feeds) on the frequency of respiratory events in preterm infants managed in a neonatal unit.

- We hypothesise that feeding interventions such as alternative positioning and pump tube feeds may reduce frequency of respiratory events in preterm infants.
- This may inform clinical practice by neonatal medical and nursing staff who are caring for this vulnerable population.

Study Population

Plain Language

The infants in this study consist of well babies who were born prematurely, less than 32 weeks' gestation, who are breathing by themselves (not needing respiratory support) and who are being fed by a feeding tube.

Inclusion Criteria

Preterm Infants < 32 weeks gestation at birth can be enrolled in the study and become eligible once they meet the additional criteria below:

- Off respiratory support for at least 5 days
 - Infants who are on low flow sub-nasal oxygen < 0.5 L/min are eligible (oxygen flow rate will not be weaned during the trial)
 - Infants who are receiving Caffeine Citrate will not be excluded, but the caffeine dose will only be adjusted for body weight during the trial and will not be discontinued during the trial regardless of gestational age
- Receiving full enteral feeds (≥ 150 mL/kg/day) for at least 5 days
- Receiving 3 hourly feeding for at least 48 hours

Exclusion Criteria

- Currently receiving respiratory support:
 - High-flow nasal cannula therapy (HFNC)
 - Continuous Positive Airway Pressure (CPAP)
 - Nasal Intermittent Positive Pressure Ventilation (NIPPV)
 - Conventional or Oscillatory Ventilation
- Significant comorbidity:
 - History of confirmed necrotising enterocolitis (NEC)
 - Past surgery or condition likely to require surgery (other than inguinal hernia)
 - Significant or symptomatic congenital heart disease
 - Congenital airway obstruction (Pierre-Robin Sequence etc.)
- Discharge likely to occur during the trial
- Receiving nutritive suck feeds (breast or bottle feeds)
- Receiving treatment for Gastro-oesophageal Reflux Disease (GORD)
- Infants for whom a decision to provide palliative care has been made

Outcomes

Plain Language

We will be measuring the number of respiratory (breathing) events, and the time spent in different oximetry (blood oxygen level) ranges.

Definitions

For the purposes of this study, the following definitions will be used:

- Respiratory event

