The correlation between two observations from the same subject (ρ) is given by $\rho = \sigma_s^2 / (\sigma_s^2 + \sigma^2)$. The more correlated the observations from the same subject (i.e. the closer ρ is to 1), the smaller the sample size required for a cross-over design compared to an equivalent parallel design. Baseline audit data showed a correlation of approximately 0.6 for the number of events and correlations approximating 0.4 for the histogram outcomes; hence the required crossover sample size is much smaller for all three outcomes of interest to achieve similar power.

A clinically significant effect was defined for each of the three outcomes based on considerations of an effect which might modify practice:

- a 40% reduction in number of respiratory events ($n_c = 87$ infants, $1 - \beta = 0.8$)
- a 50% improvement in percentage of time spent with SpO₂ \geq 88% ($n_c = 79$ infants, $1 - \beta = 0.8$)
- a 50% reduction in percentage of time spent with SpO₂ < 80% ($n_c = 108$ infants, $1 - \beta = 0.8$)

A sample size of 90 infants would produce a study with 80% power to compare both primary outcomes, and 70% power to compare the secondary outcome.

Design Consultation

Consultation has been sought from a senior statistician at Griffith University (Gold Coast, Australia) and through a private Consultant Statistician (Data Analysis Australia Pty Ltd) which has guided design. One of the associate researchers is a consultant neonatologist with experience in education and research, and has been actively involved in the proposal design and offered clinical perspective on design parameters and outcomes. We have also sought and utilised advice from the Clinical Director of the Newborn Care Unit in which the study is taking place, as well as other neonatologists in the unit, particularly in relation to defining clinically significant effect sizes.

Analysis

A mixed effect model will be employed to analyse this crossover study. This approach has the advantages that all three treatment effects for a given outcome can be modelled together, and incomplete records in the case of dropouts can still contribute to the model fit and the method can handle unbalanced data. Standard analysis methods exclude incomplete records and so the study can quickly become underpowered when patients don't complete all treatments.

Consent

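### An unadjusted 5% level for four primary tests (two outcomes, two contrasts with control) gives about a 13–17% chance of at least one false primary result

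*Protocol*

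**What the plan says.** The level is fixed in the protocol's Size and Power Considerations: "We will use a 5% significance level", and the sentence goes on to apply it to every comparison. The next sentence adds "The expected sample was sized using a two-sided test".

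The outcome list in the same section marks two outcomes as primary: "Number of respiratory events (primary outcome") and "Percentage of time spent with SpO₂ < 80% over the 24h testing period (primary outcome"). The Primary Outcomes section agrees and ranks neither.

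Table 1 gives one control (A) and two interventions (B, position; C, feed rate). Under Study Design, "each infant will experience each of the three test conditions in a sequence which is randomised". The hypothesis covers both interventions and puts neither first: "We hypothesise that feeding interventions such as alternative positioning and pump tube feeds may reduce frequency of respiratory events".

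The Analysis section names a mixed effect model in which "all three treatment effects for a given outcome can be modelled together". It names no overall test, order of testing or adjustment.

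**The concern.** Two primary outcomes and two contrasts with control (B vs A, C vs A) make four primary tests. Each carries its own 5%, and nothing prevents any single significant one from being reported as a positive primary finding. The probability of at least one false primary result is then well above the 5% a reader would take from the text. The protocol says the results may inform clinical practice, and it chose its effect sizes as ones that might change practice, so one chance finding for either intervention could be acted on. The sample size rests on the same unadjusted level, so a later adjustment would also lower the power that the protocol reports.

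**Working it through.** **Inputs from the protocol.** Two-sided α = 0.05 per comparison; two primary outcomes; contrasts B vs A and C vs A; n_c = 87 (events) and n_c = 108 (SpO₂ below 80%), each for 80% power; planned N = 90.

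**Assumptions.** The correlation r between the two outcomes is not given, so it is varied. All treatment effects are zero (global null). Any one significant primary contrast counts as a claim.

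**Step 1: the plan's own power figure.** The within-subject variance is not printed, so n_c cannot be rebuilt from first principles. Equation 1 does allow power at N = 90 to be scaled from each n_c:

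power = Φ[(1.960 + 0.842) × √(90/n_c) − 1.960]

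- Events: 2.802 × √(90/87) = 2.849; Φ(2.849 − 1.960) = 81.3%. This agrees with the stated 80%.
- SpO₂ below 80%: 2.802 × √(90/108) = 2.557; Φ(2.557 − 1.960) = 72.5%. The protocol states 80% for both primaries. That mismatch is a separate matter, but 72.5% is the correct starting point for the power figures below.

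**Step 2: family-wise error as written.** If the four tests were independent, the error would be 1 − 0.95⁴ = 18.5%. They are not independent: B vs A and C vs A share the control, which gives a correlation of 0.5 within an outcome. I simulated three equal-variance condition means on two outcomes with correlation r (2,000,000 draws, each test two-sided at 5%). In the last column, benefit means B or C better than A on either primary.

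| r | At least one false result, either direction | At least one false benefit |
|---|---|---|
| 0 | 17.3% | 8.9% |
| 0.5 | 16.1% | 8.1% |
| 0.7 | 14.9% | 7.4% |
| 0.9 | 12.6% | 6.3% |

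The two-sided figures compare with 5%, a ratio of 2.5 (12.6/5) to 3.5 (17.3/5). The benefit figures compare with 2.5%, the share of a two-sided 5% test that lies in the favourable direction, a ratio of 2.5 (6.3/2.5) to 3.6 (8.9/2.5).

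One outcome alone with two contrasts gives 9.1% two-sided and 4.5% for false benefit. So even perfectly correlated outcomes would not bring the error back to nominal.

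**Step 3: power under control of the error.** The scaling is that of Step 1, with the critical value c replacing 1.960 in the subtracted term:

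| Rule (first step) | c | Events | SpO₂ below 80% |
|---|---|---|---|
| Unadjusted | 1.960 | 81.3% | 72.5% |
| Dunnett, two contrasts | 2.21 | 73.8% | 63.5% |
| Holm, two contrasts (0.025) | 2.241 | 72.8% | 62.4% |
| Holm, four tests (0.0125) | 2.498 | 63.7% | 52.4% |

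For example, events under Dunnett: Φ(2.849 − 2.21) ≈ 73.8%. The SpO₂ figures do not include the further loss from any gate.

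**The case against.** The strongest objection is that multiplicity procedures and contrast hierarchies are usually set in the statistical analysis plan, which is not at hand, and that the Analysis section fixes no contrast set. That would answer a complaint about silence, but here the protocol states a rule: 5% for every comparison. An analysis plan that adjusted would contradict that sentence and lower the stated power, so the protocol text has to change either way.

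A second objection is that position and feed rate are separate questions which need not form one family. This is debatable. Taken one intervention at a time, two outcomes at 5% each still give about 7% (r = 0.9) to 10% (r = 0).

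Two stronger readings should be resisted.

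- A reader might count six tests and quote 23%. That needs B vs C as a primary contrast, which the protocol nowhere names; Table 1 labels A as control and the hypothesis is about reducing events. It also needs zero correlation between the primaries, although the event count includes desaturations below 80% and the other primary is time below 80%.
- A reader might say that a false claim of benefit has a 13–17% probability. Those figures count rejections in both directions, and apparent harm cannot support a claim that feeding interventions reduce events. The benefit figure is 6–9%.

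**Conclusion.** The point holds for four primary tests. Followed as written, the protocol carries about a 13–17% two-sided chance of at least one false primary result, or about 6–9% for a false benefit against a nominal 2.5%. These figures assume no true effects, any single significant contrast counting as a claim, and r between 0 and 0.9. Because the two primaries share the signal below 80%, r = 0 is unlikely and the lower part of each range is the more plausible. The error would be higher only if B vs C were also treated as primary, and lower if both primaries had to succeed; the protocol states neither. This should be corrected, and text alone is enough.

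**What to change.** Replace the blanket 5% sentence with a pre-specified rule that holds overall two-sided error at 5% across the four primary tests. Either option works:

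1. **Ordered.** Test respiratory events first, B vs A and C vs A, by Holm or Dunnett at overall 5%. Test SpO₂ below 80% only if both events contrasts succeed, again by Holm at 5%; otherwise make it a secondary outcome. The gate must say explicitly that one success out of two does not open it.
2. **Unranked.** If the sponsor prefers not to rank the primaries, apply Holm across all four tests.

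In both, state that B vs C is secondary. Which outcome goes first is the sponsor's choice, since the protocol ranks neither.

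Restate power at N = 90. Under option 1, events have about 73–74% per contrast at the first step (about 81% unadjusted by the same scaling; 80% stated). SpO₂ below 80% has about 62–64%, down from about 72% unadjusted, before the further loss from the gate. Under option 2, first-step power is about 64% for events and 52% for SpO₂ below 80%.

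The cost is one paragraph of text and lower stated power. No extra infants are needed unless the sponsor wants to restore 80%.

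### The power sentence for 90 infants contradicts the protocol's own list of required sample sizes for both SpO₂ outcomes

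*Protocol*

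**What the plan says.** The outcome roles are the same in two places. The Primary Outcomes and Secondary Outcomes sections, and the list of pilot measures under Size and Power Considerations, all treat events and low saturation as primary: "Number of respiratory events (primary outcome") and "Percentage of time spent with SpO₂ < 80% over the 24h testing period (primary outcome"). Time with SpO₂ at or above 88% is the secondary outcome.

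The basis for sizing is also stated: "We will use a 5% significance level ($\alpha = 0.05$) for all comparisons", and "The expected sample was sized using a two-sided test". In Equation 1, "n_c is the minimum total sample size required for cross-over design".

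The protocol then lists the number needed for 80% power on each outcome:

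- 87 infants for a 40% reduction in events (primary);
- 79 infants for a 50% improvement in time at or above 88% (secondary);
- 108 infants for a 50% reduction in time below 80% (primary).

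The conclusion follows directly: "A sample size of 90 infants would produce a study with 80% power to compare both primary outcomes, and 70% power" for the secondary outcome.

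**The concern.** No calculation is needed to see the conflict. A sample of 90 is smaller than 108, so by the list it cannot give 80% power for time below 80%. It is larger than 79, so by the list it must give more than 80% for time at or above 88%. The sentence says the opposite for both saturation outcomes. Only its claim for respiratory events agrees with the list.

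This sentence is the justification for the planned sample size. If the list is right, a non-significant result on the low-saturation primary would be read as coming from a comparison with a 20% chance of missing the target effect, when that chance is about 27.5% (100% − 72.5%). The power for the secondary outcome would be understated at the same time.

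**Working it through.** **Inputs, all from Size and Power Considerations.** Two-sided α = 0.05, so z = 1.960. Power of 80% behind each listed n_c, so z = 0.842. Planned N = 90. Listed n_c = 87, 108 and 79.

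**Formula.** Equation 1 is n_c = 2(z_α/2 + z_β)²σ²/Δ². For fixed σ² and Δ, the standardised effect grows with the square root of the sample size. Power at N can therefore be scaled from each listed n_c:

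Power(N) = Φ[(1.960 + 0.842) × √(N/n_c) − 1.960]

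The within-subject variance is not stated, but it cancels, as does the exact definition of Δ. Setting N = n_c returns Φ(0.842) = 80%, which is the protocol's own figure for each list entry.

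**Results at N = 90, taking the list and the outcome labels as printed:**

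| Outcome | Role | n_c | 2.802 × √(90/n_c) − 1.960 | Power | Stated |
|---|---|---|---|---|---|
| Respiratory events | Primary | 87 | 2.850 − 1.960 = 0.890 | 81.3% | 80% |
| SpO₂ below 80% | Primary | 108 | 2.558 − 1.960 = 0.598 | 72.5% | 80% |
| SpO₂ at or above 88% | Secondary | 79 | 2.991 − 1.960 = 1.031 | 84.9% | 70% |

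The figure for events is reproduced within about one percentage point. The other two are not.

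**Sensitivity to method.** With a one-sided α of 0.05, or a noncentral t distribution with 89 or 178 degrees of freedom, power for SpO₂ below 80% lies between 71.6% and 73.4%, and for SpO₂ at or above 88% between 84.1% and 84.9%. No variant recovers the stated 80% and 70%.

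**What would make the sentence true.** Suppose 79 belonged to time below 80% and 108 to time at or above 88%. The same formula would then give 81.3% and 84.9% for the two primaries and 72.5% for the secondary, which fits the sentence if 80% is read as a minimum and 70% as a rounded figure. So one exchange of the two saturation outcomes, in either the list or the sentence, removes the conflict.

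**The case against.** The strongest reply is that the contradiction does not show which text is wrong. A reader might infer that the sentence is the error and that one primary outcome is certainly underpowered. The protocol does not support that inference. Its list of pilot measures runs events, below 80%, at or above 88%. The list of required sizes, like the Effect Size section, runs events, at or above 88%, below 80%. If 87, 79 and 108 were carried over from output in the first order, the labels on 79 and 108 are exchanged, the sentence is right, and no primary falls short. A third possibility is that the primary and secondary roles changed after the sizing was done. The variances that would decide the matter are not given. This objection stands: the direction of the error has to be stated conditionally.

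A second reply is that the gap is small beside the uncertainty in the inputs. The variances come from 10 infants measured on three days, or about 10 × (3 − 1) = 20 within-subject degrees of freedom. A 95% interval for such a variance runs from about 0.59 to 2.09 times the estimate, which turns 108 into roughly 63 to 225. That is a fair caution against treating 72.5% as precise. It does not reconcile a list and a sentence that draw on the same pilot estimates.

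A reader might also infer that a margin of three infants (90 − 87) leaves the trial exposed to dropout. The Analysis section does not support this. It raises loss of power as a problem of standard methods that discard incomplete records, and plans a mixed model in which such records still contribute. Dropouts cannot be counted as contributing nothing, and the point here does not rest on them.

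**Conclusion.** The protocol contradicts itself: the power sentence cannot be true together with the list above it and the outcome labels. This follows from the protocol's own figures, with no outside assumption and no dependence on the choice of power method.

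The size of the error is conditional. If the list and the outcome labels are right, 90 infants give about 81% power for respiratory events, about 72–73% rather than 80% for the SpO₂ below 80% primary, and about 85% rather than 70% for the secondary. If the labels on 79 and 108 were exchanged, the sentence is sound and the list is wrong. If the hierarchy changed after sizing, the sentence is out of date, and under the present labels the 72–73% applies to a primary outcome. The protocol alone cannot tell these cases apart.

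**What to change.** 1. Check 79 and 108 against the variance-components output from the pilot, and confirm which saturation outcome each belongs to.
2. Correct whichever text is wrong (the list, the power sentence or the outcome labels) so that all three agree.
3. Restate the power at N = 90 separately for each outcome, in place of one figure for both primaries.

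If the list and the labels stand, the sentence could read: with 90 infants, power is about 81% for the number of respiratory events, about 73% for time with SpO₂ below 80% (primary), and about 85% for time with SpO₂ at or above 88% (secondary). The figures should not be written in before step 1, because if the list is mislabelled they would replace a correct sentence with a wrong one.

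The cost is a look at existing output and a corrected sentence or list entry in an amendment. Neither the sample size nor the outcome hierarchy needs to change to put the statement right. The downside, if the list stands, is that the stated power for one primary outcome becomes less favourable.
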